1.0 Objectives*

- 1.1 This study aims to investigate the effect of abobotulinum toxin A on the symptoms of Raynaud's phenomenon. By studying the effect of abobotulinum toxin A on Raynaud's symptoms among a more diverse population we hope to provide insight into the patients most likely to benefit from abobotulinum toxin A.
- 1.2 Our hypothesis is that hands that receive injections of abobotulinum toxin A will experience greater relief from symptoms compared to hands which do not

2.0 Background*

- 2.1 Raynaud's phenomenon affects up to 20% of the population, and is commonly associated with many autoimmune and inflammatory diseases.¹ It affects over 90% of scleroderma patients, but also affects over 10% of patients with systemic lupus, dermatomyositis, rheumatoid arthritis, and primary Sjögren's syndrome.² Additionally, Raynaud's phenomenon associated with an immunological disease is commonly has severe progression and can lead to amputation of the affected digits.² Symptoms of Raynaud's phenomenon are a result of worsened circulation to the extremities, particularly in the hands. A decrease in circulation leads to ischemia of the tissues, causing pain and functional limitations as well as ulcers and gangrene.³ This can prove extremely debilitating to patients, reducing quality of life. Treatment options include medications which seek to increase vasodilation, most commonly calcium channel blockers.⁴ If patients fail to improve under pharmacological interventions, surgery is often required to alleviate symptoms or remove ischemic and gangrenous tissue.⁵ However, studies have shown that botulinum toxin (BoNT) reduces symptoms in certain patient populations with Raynaud's phenomenon.⁶⁻⁹
- 2.2 BoNT works as a vasodilator by blocking the release of neurotransmitters and thereby decreasing the muscular sympathetic response.¹⁰ Therefore, the muscle relaxes and in the case of vascular muscle, allows for vasodilation of the blood vessel. Although approved by the FDA to treat muscle spasms, the specific use of BoNT for the treatment of Raynaud's phenomenon is not recognized.¹¹ Despite its off-label use, multiple studies support the benefits of using BoNT as a treatment for Raynaud's phenomenon.¹²
- 2.3 A 2014 study by Neumeister and colleagues shows BoNT improves blood flow in the hand as well as reduces pain and improves function.⁷ However, studies have focused on specific patient populations, such as that of scleroderma or systemic sclerosis.^{6,13} Additionally, studies have lacked a coordinated methodology with some lacking double-blind experimentation, a control group, or appropriate treatment dosage. Our prospective double-blind

PROTOCOL TITLE: The Effect of Abobotulinum Toxin A on the Symptoms of Raynaud's Phenomenon, a Double-Blind Randomized Placebo-Controlled Trial

randomized control trial seeks to compare a single formulation of BoNT, abobotulinum toxin A (Dysport), to a placebo saline group, studying the effect of BoNT on Raynaud's symptoms among a more diverse population to provide insight into the patients most likely to benefit from BoNT. Additionally, we hope that if we have positive findings that this data could be used to justify insurance coverage of BoNT in Raynaud's phenomenon. With BoNT costing hundreds to thousands of dollars per treatment, it can prove a financial burden for patients relying on BoNT for relief from symptoms and prevention of amputation.¹⁴ Preliminary findings from this study could be used to justify further studies for a new indication for Raynaud's phenomenon thus improving patients' chances for coverage and ease of access.

3.0 Inclusion and Exclusion Criteria*

3.1 For this study, patients at UCF Health will be screened in person for eligibility using the following inclusion criteria listed in 3.2. Screening will be performed by [name] or [name]. (See attached "Eligibility Screening")

3.2 Screening Criteria

- Inclusion Criteria:

- Male or female adult between 18 and 80 years of age
- Must have health insurance
- Must have a current diagnosis of Raynaud's phenomenon

- Exclusion Criteria:

- Allergy to abobotulinum toxin A or its components
- Diagnosis of myasthenia gravis
- Previously received abobotulinum toxin vaccine
- Previously undergone upper extremity vascular surgery (including surgical sympathectomy)
- Currently receiving aminoglycoside antibiotics
- Received abobotulinum toxin A treatment in either hand in the past 6 months
- Pregnant women
- Women currently breastfeeding
- Current tobacco smoker (use in the past 12 months)
- Unable to read and speak English

PROTOCOL TITLE: The Effect of Abobotulinum Toxin A on the Symptoms of Raynaud's Phenomenon, a Double-Blind Randomized Placebo-Controlled Trial

- Adults unable to consent
- Individuals who are not yet adults (infants, children, teenagers)Prisoners

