9.0 Procedures Involved*

9.1 Our study is a double-blind randomized placebo-controlled trial.

- Treatment arm: Injection of 300 units of abobotulinum toxin A in 10 ml of non-bacteriostatic normal saline to chosen hand.
- Control arm: Injection of 10 ml of non-bacteriostatic normal saline to chosen hand.
- Randomization will be determined by coin flip as follows:
 - Heads: Right hand – treatment arm; Left hand – control arm.
 - Tails: Right hand – control arm; Left hand – treatment arm.

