11.0 Data Management* and Confidentiality

11.1 The data will be analyzed for significant differences with aid of a statistician. A significance level of 0.05 will be used for statistical hypothesis testing. The results of the data analysis will be graphed for each parameter.

- Categorical variables, such as sex (male and female), age, and comorbidities (e.g., scleroderma) will be reported descriptively, as frequencies and percentages. Outcomes in this study are visual analog scale for pain (VAS Pain), Raynaud's Condition Score (RCS), and the Disabilities of the Arm, Shoulder and Hand Score (QuickDASH), which are continuous variables. In addition, the number of digital ulcers and number of attacks/episodes per week, which are discrete variables, will be measured as outcomes. These continuous and discrete variables will be expressed as mean \pm standard deviation, with standard error of the mean (SEM).
- To assess between group differences, an Independent samples t-tests will be conducted separately for the three time periods: baseline, 1-month, and 3-month. Additionally, a dependent sample t-test will be used to assess within-group differences from 1-month to 3-month, separately for the experimental and control groups. It is possible to use the baseline measurement as a covariate in an analysis of covariance (ANCOVA) and/or in a repeated measures ANOVA. Thus, the researchers will also explore these additional analyses if the sample size permits.
- All tests will be two-sided, and p-values < 0.05 will be considered statistically significant. Statistical analyses will be conducted using SPSS 24.0 (IBM; Chicago, IL).

PROTOCOL TITLE: The Effect of Abobotulinum Toxin A on the Symptoms of Raynaud's Phenomenon, a Double-Blind Randomized Placebo-Controlled Trial

11.2 Utilizing the statistical software G*Power it was determined that 16 patients would be needed to detect a 2-point difference in the RCS among the treatment arms. (G*Power) This assumes a standard deviation of 1.92, power of 0.8, alpha of 0.05, and effect size (d) of 1.04. (Merkel)

11.3 Data will be managed as follows:

- Data will be stored in the secure HIPAA-compliant database called REDCap.
- Unique identifiers will be created using sequential numbers (i.e. 1, 2, 4 etc.).
- No data collection instrument in REDCap will contain identifying information

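### The 6-month washout names only abobotulinum toxin A; recent hand injection of another botulinum toxin product is not excluded by it and could dilute the between-hand contrast

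*Combined protocol and SAP*

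**What the plan says.** Section 3.2 contains one washout criterion: "Received abobotulinum toxin A treatment in either hand in the past 6 months". The other toxin-related exclusions are allergy to the study drug or its components and "Previously received abobotulinum toxin vaccine". No inclusion or exclusion criterion mentions treatment with a different botulinum toxin product.

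The background is written at class level. Section 2.2 states that "BoNT works as a vasodilator by blocking the release of neurotransmitters and thereby decreasing the muscular sympathetic response". Section 2.3 says the trial seeks to "compare a single formulation of BoNT, abobotulinum toxin A (Dysport), to a placebo saline group", which separates the product from the class. The same section remarks on the cost of BoNT that "it can prove a financial burden for patients relying on BoNT for relief from symptoms and prevention of amputation".

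Section 9.1 randomizes hands within a patient by coin flip ("Heads: Right hand – treatment arm; Left hand – control arm", and the reverse for tails). Section 11.1 commits to independent-samples t-tests at baseline, 1 month and 3 months. Analysis of covariance with baseline as covariate is to be explored only if the sample size allows. Section 11.2 states that "16 patients would be needed to detect a 2-point difference in the RCS among the treatment arms".

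**The concern.** If the vasodilator effect belongs to the class, a recent injection of another product could leave residual effect in a study hand, just as the named product could. The criterion as worded does not screen for this.

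The design is exposed because the control is the patient's other hand. Residual effect in both hands leaves less room for a difference between toxin and saline. Residual effect in one hand can fall in either arm, depending on the coin. The committed tests do not adjust for baseline, so nothing in the main analysis would correct for it. With about 16 patients, each affected patient is one-sixteenth of the comparison.

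**Working it through.** **Inputs.** From section 11.2: target difference 2 points on the Raynaud's Condition Score (RCS), SD 1.92, power 0.8, alpha 0.05, d = 1.04, 16 patients. From section 11.1: two-sided independent-samples t-test. Each patient supplies one hand per arm (section 9.1), so n = 16 hands per arm. The number of affected patients k and the share r of the contrast that remains in them are assumptions; the documents give neither.

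**Step 1: reproduce the plan's figure.** d = 2/1.92 = 1.04. The noncentrality is d × √(n/2) = 1.0417 × √8 = 2.95, with 30 degrees of freedom and critical t = 2.042. The noncentral t distribution gives power 0.81 at 16 per arm and 0.79 at 15 per arm, so 16 is the smallest n that reaches 0.80. The stated 16 is reproduced.

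**Step 2: residual effect in both hands of k patients.** The mean difference becomes 2 × [1 − (k/16)(1 − r)]. For k = 2 and r = 0 this is 2 × (1 − 2/16) = 1.75, with noncentrality (1.75/1.92) × √8 = 2.58 and power 0.70.

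| k of 16 | Difference, no contrast left (r = 0) | Power | n per arm for 80% | Difference, half left (r = 0.5) | Power | n per arm for 80% |
|---|---|---|---|---|---|---|
| 0 | 2.00 | 0.81 | 16 | 2.00 | 0.81 | 16 |
| 1 | 1.875 | 0.76 | 18 | 1.938 | 0.79 | 17 |
| 2 | 1.75 | 0.70 | 20 | 1.875 | 0.76 | 18 |
| 4 | 1.50 | 0.57 | 27 | 1.75 | 0.70 | 20 |

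**Step 3: simulation check.** This used 40,000 simulated trials per scenario, residual effect assumed to equal the full 2 points and not to add to fresh toxin, and no correlation between hands. Residual effect in both hands of 2 or 4 patients gave mean differences of 1.75 and 1.51 and power of 0.68 and 0.53. These powers are slightly below step 2 because mixing affected and unaffected saline hands also widens their spread. Residual effect in one hand, with the coin deciding its arm, gave 1.88 and 1.75, with power 0.75 and 0.68.

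With a between-hand correlation of 0.5, power of the independent test starts at 0.89. It falls to 0.74 or 0.54 (both hands) and to about 0.82 or 0.73 (one hand).

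**Step 4: direction.** In every scenario run, the average difference shrinks or stays the same. If residual effect in one hand did add to fresh toxin, each such patient would move the mean difference by 2/16 = 0.125 points, up or down with equal probability. That is chance imbalance, not systematic bias.

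**The case against.** The strongest case against is that exposure is probably rare and the loss hypothetical. The sentence on patients relying on BoNT is a general remark about cost, not a description of this site. The background also calls the use off-label, at hundreds to thousands of dollars per treatment, which suggests few recent users. This stands: k may be zero or small, and k = 4 would mean a quarter of the sample. In the other direction, section 15.1 lists free treatment as a possible benefit, which gives existing users a reason to enrol. Neither argument yields a number.

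The exclusion may also be only loosely worded. The vaccine criterion uses the same product name, which suggests that a broader term may have been intended; this is inference only. The eligibility and medical history forms are attachments that were not available, so they may already ask about other products. A baseline between-hand test is planned and could reveal a one-hand imbalance, but it would not show residual effect present in both hands.

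A reader might infer four stronger points that the documents do not support:

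- **That the gap biases the trial towards toxin.** The coin flip rules out a systematic tilt.
- **That the protocol's own reason for the washout covers other products.** Section 3.2 gives no reason for it. Carry-over of effect is an inference from the class-level mechanism in section 2.2.
- **That prior users would recognise the toxin hand.** The documents say nothing on this, and a wider 6-month exclusion would still admit people treated earlier.
- **That the trial is underpowered as planned.** Power is 0.81 under its own assumptions; the lower figures apply only if such patients enrol.

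**Conclusion.** The point holds in a limited form. The washout is narrower than the class-level rationale, and the available text does not close the gap. A patient recently treated in the hands with another product is not excluded by this criterion, although every other criterion must still be met.

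The expected harm is attenuation of the between-hand difference, with added chance imbalance when one hand was treated before. One affected patient would take power from 0.81 to between 0.76 (no contrast left) and 0.79 (half left), just under the stated 0.8. Two would take it to between 0.70 and 0.76. These figures rest on assumed numbers of patients and an assumed loss of contrast. They illustrate sensitivity and do not forecast what will happen. Severity is low.

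**What to change.** Replace the product name in the washout criterion with any botulinum toxin product, leaving the reference to either hand and the protocol's own 6-month interval unchanged. Align the eligibility screening form with the new wording. If the medical history form does not already do so, add an item for earlier botulinum toxin exposure by product, date and hand; the data list in section 9.4 names none.

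The planned 16 patients do not change. The cost is one phrase in an amendment and possibly one or two extra screen failures, against planned enrolment of 20 to obtain 16 (section 4.1).

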4.0 Study-Wide Number of Subjects*

4.1 We plan on enrolling 20 subjects with the aim to accrue 16 subjects who successful screen for eligibility for the study. This number was derived from a power analysis performed with [name].

5.0 Study-Wide Recruitment Methods*

5.1 Not applicable. This is not a multicenter research study and research will only be conducted at UCF Health clinics in Lake Nona. Local recruitment methods are described in section 19.0 Setting.

6.0 Multi-Site Research*

6.1 Not applicable. This is not a multi-site research project. Research will only be conducted at the UCF Health clinic in Lake Nona.

7.0 Study Timelines*

7.1 Subjects are expected to participate in this study for a total of twelve months. During these twelve months, subjects will be required to come to UCF Health Clinic at [name] for a total of five appointments:

- Baseline appointment: 1 hour
- 48-hours follow-up phone call: 5 minutes
- 1-month follow-up appointment: 15 minutes
- 3-month follow-up appointment: 15 minutes
- 6-month follow-up appointment: 15 minutes
- 12-month follow-up appointment: 15 minutes
- For the first 3 months subjects will be asked to complete a weekly survey either online or on paper to bring in.
- For the final 9 months subjects will be asked to complete a monthly survey either online or on paper to bring in.
- Ten months is the anticipated length of time to recruit participants.
- The study is expected to be completed by October 2019.

8.0 Study Endpoints*

8.1 Primary endpoints: Participation in the study will end 12 months after the baseline visit or if the patient elects to be removed from the study, whichever comes first.

PROTOCOL TITLE: The Effect of Abobotulinum Toxin A on the Symptoms of Raynaud's Phenomenon, a Double-Blind Randomized Placebo-Controlled Trial

- 8.2 Primary and secondary safety endpoints: adverse reaction to the abobotulinum toxin A solution. If a participant develops a reaction, he or she will be given the option to withdraw but will not be required to withdraw, unless life threatening.

9.0 Procedures Involved*

9.1 Our study is a double-blind randomized placebo-controlled trial.

- Treatment arm: Injection of 300 units of abobotulinum toxin A in 10 ml of non-bacteriostatic normal saline to chosen hand.
- Control arm: Injection of 10 ml of non-bacteriostatic normal saline to chosen hand.
- Randomization will be determined by coin flip as follows:
 - Heads: Right hand – treatment arm; Left hand – control arm.
 - Tails: Right hand – control arm; Left hand – treatment arm.

9.2 Timeline

- Subject visits
 - The abobotulinum toxin A solution and saline solution will be prepared the same day as the subject's baseline visit
 - Baseline Visit
 - a. Minute 00-20:
 - i. Screening and consent process in screening room
 - b. Minute 20-40:
 - i. Assessment of baseline Raynaud's symptoms via Baseline Case Report (attached) and photographs will be taken of both hands
 - ii. Administration of abobotulinum toxin A solution and normal saline solution
 - c. Minute 40-60:
 - i. Review post-procedure instructions and how to complete Brief Follow-up Case Reports. Observe subject for any adverse reaction.
 - 48-hour follow-up phone call:

[figure not shown]
PROTOCOL TITLE: The Effect of Abobotulinum Toxin A on the Symptoms of Raynaud's Phenomenon, a Double-Blind Randomized Placebo-Controlled Trial

- a. Minute 0-5:
 - i. Brief phone call to assess for any adverse reactions.
- 1-month (+/- 8 days) Follow-up
 - a. Minute 00-15:
 - i. Assessment of Raynaud's symptoms via Follow-up Case Report (attached) and photographs will be taken of both hands
- 3-month (+/- 15 days) Follow-up
 - a. Minute 00-15:
 - i. Assessment of Raynaud's symptoms via Follow-up Case Report (attached)
- 6-month (+/- 15 days) Follow-up
 - a. Minute 00-15:
 - i. Assessment of Raynaud's symptoms via Follow-up Case Report (attached) and photographs will be taken of both hands
- 12-month (+/- 15 days) Follow-up
 - a. Minute 00-15:
 - i. Assessment of Raynaud's symptoms via Follow-up Case Report (attached) and photographs will be taken of both hands
- Subject surveys
 - Months 0-3:
 - a. Every week the subjects will be asked to complete the Brief Follow-up Case Report either online or on a paper version given to the subject.
 - Months 4-12
 - a. Every month the subjects will be asked to complete the Brief Follow-up Case Report either online or on a paper version given to the subject
- Solution preparation

PROTOCOL TITLE: The Effect of Abobotulinum Toxin A on the Symptoms of Raynaud's Phenomenon, a Double-Blind Randomized Placebo-Controlled Trial

- 300 unit vials of abobotulinum toxin A will be reconstituted with 10 ml of non-bacteriostatic normal saline yielding a final concentration of 30 units per 1 ml.
- The solutions will be drawn up in 1 cc syringes utilizing a 25g needle by [name]. The needle will then be replaced with a capped 30g ½ inch needle.
- All solutions will be prepared and drawn up by [name] the day of use after consent has been obtained and discarded immediately after use.
- The syringes will be labeled with a red or blue label for randomization by [name], [name], or [name].
- Screening and consent:
 - Each participant will sit down with the principal investigator to discuss the study in depth and review the screening criteria. After all risks, benefits, alternatives, and questions have been discussed consent will be obtained.
 - After the informed consent form is signed, the eligibility screening portion of the case report form will be filled out by the principal investigator with the research subject. If necessary, a pregnancy test will be performed.
- Administration of study solution:
 - 10 sites on each palm will be used (see image below):
 - a. Two at the base of the thumb
 - b. Three in the middle of the palm
 - c. Five at the proximal base between each finger

PROTOCOL TITLE: The Effect of Abobotulinum Toxin A on the Symptoms of Raynaud's Phenomenon, a Double-Blind Randomized Placebo-Controlled Trial

- The participants' sites of administration will be cleansed with isopropyl alcohol before administration. Needles will be introduced at a 90-degree angle subcutaneously. 1 ml of solution will be injected per site.
- A board-certified dermatologist, [name], will be administering all solutions to minimize risks for participants.
- Subjects will be given the clinic number and asked to call if they think they are experiencing any adverse effects.
- Subjects will be evaluated either in person or over the phone 1 month and 3 months after treatment.
- Disposal protocol:
 - After use, needles will be disposed of in red sharps container according to UCF Health policy.
 - After use, urine samples will be disposed of in the toilet according to UCF Health policy.

9.3

- Risk Management:
 - Participants will be directly observed during the administration of the botulinum toxin and placebo for any adverse events. An anaphylaxis kit is available in clinic should any participant experience such an event. The principal investigator is certified in basic cardiopulmonary life support and an AED is present in the facility. Participants will be provided with the phone number of the

PROTOCOL TITLE: The Effect of Abobotulinum Toxin A on the Symptoms of Raynaud's Phenomenon, a Double-Blind Randomized Placebo-Controlled Trial

PI should any issues related to participation in the study arise.

- Abobotulinum toxin A is the only drug used in this research study. It is currently FDA-approved for cervical dystonia, moderate to severe glabellar lines, upper limb spasticity, and lower limb spasticity.
- The following are the source documents (see attached):
 - a. Subject ID Assignment Log
 - b. Screening and Enrollment Log
 - c. Drug Accountability Log
 - d. Eligibility Form
 - e. Demographics Form
 - f. Medical History Form
 - g. Baseline Case Report Form
 - h. Follow Up Case Report Form
 - i. Brief Follow Up Case Report Form
 - j. Adverse Event Form

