14.0 Risks to Subjects*

14.1 There is no major anticipated risk associated with the study. However potential risks to the subject include:

- Discomfort and pain upon injection and infiltration of abobotulinum toxin A or normal saline
- Temporary muscle weakness that may last 6 weeks
- Negligible bleeding or bruising

PROTOCOL TITLE: The Effect of Abobotulinum Toxin A on the Symptoms of Raynaud's Phenomenon, a Double-Blind Randomized Placebo-Controlled Trial

- Minimal risk of infection (<1%)¹⁶
- Allergy to abobotulinum toxin A solution (<1%)
- Furthermore, true allergy to abobotulinum toxin A is extremely rare.¹⁷

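### The protocol text states no scheduled adverse-event enquiry after the 48-hour call and plans no toxin-hand versus saline-hand comparison of harms, so later harms may be under-counted

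*Combined protocol and SAP*

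**What the plan says.** All references are to the combined protocol and SAP.

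- **Endpoint (8.2).** "Primary and secondary safety endpoints: adverse reaction to the abobotulinum toxin A solution". The saline hand is not named.
- **Design (9.1).** Each patient receives toxin in one hand and saline in the other, by coin flip and under double-blinding: "Heads: Right hand – treatment arm; Left hand – control arm", and the reverse for tails.
- **Injection day.** Section 9.3 covers both solutions: "Participants will be directly observed during the administration of the botulinum toxin and placebo for any adverse events". After the injections, minutes 40 to 60 of the baseline visit include the instruction "Observe subject for any adverse reaction".
- **48 hours (9.2).** "Brief phone call to assess for any adverse reactions".
- **Later visits (9.2).** The entry at 1, 6 and 12 months is "Assessment of Raynaud's symptoms via Follow-up Case Report (attached) and photographs will be taken of both hands". The 3-month entry is the same without the photographs.
- **Between visits (9.2).** The Brief Follow-up Case Report is completed weekly in the first three months and monthly from months 4 to 12. Patients are also "asked to call if they think they are experiencing any adverse effects". The next bullet has them evaluated at 1 and 3 months, in person or by telephone, without saying for what.
- **Expected harm (14.1).** "Temporary muscle weakness that may last 6 weeks".
- **Data and analysis.** Section 9.3 lists an Adverse Event Form among the source documents. The data list in 9.4 has no adverse-event item, and 11.1 has no adverse-event summary. The halfway review in 12.1 uses pain, RCS, QuickDASH, ulcers and attacks.

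**The concern.** Two features of the text work against a usable account of harm.

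The first is timing. The protocol expects that one harm may last 6 weeks, but the last contact it describes as an adverse-event check is on day 2. If the later contacts ask only about Raynaud's symptoms, weakness that appears or persists after day 2 is recorded only if the patient volunteers it.

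The second is the comparison. Both hands are injected with the same volume at the same number of sites, so discomfort, bruising or weakness in the saline hand shows what injection alone does. An endpoint worded around the toxin solution, with no instruction to record the hand and no table by hand, leaves that information unplanned. It also fits poorly with blinding: to classify a local reaction as due to the toxin solution, one must know which hand received it.

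At stake is whether the trial can describe local harms completely and separate toxin effects from injection effects.

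**Working it through.** **Plan's own figures.** The plan gives no expected adverse-event rate and no safety precision target, so there is no safety figure to reproduce. The only sizing figure (11.2) is 16 patients for a 2-point RCS difference with SD 1.92: d = 2/1.92 = 1.04. A two-sided independent-samples t-test at 0.05 with 80% power needs 15.5, so 16 per arm (16 toxin hands and 16 saline hands). The figure reproduces, and it matters here only as the number of patients.

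**1. Which contacts have a stated adverse-event purpose**

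| Contact | Stated content | Adverse-event enquiry stated? |
|---|---|---|
| During injection (9.3) | Observation, toxin and placebo | Yes |
| Baseline, minutes 40–60 (9.2) | Observation, instructions | Yes |
| 48-hour call (9.2) | Adverse reactions | Yes |
| 1, 3, 6, 12 months (9.2) | Raynaud's symptoms; photographs except at 3 months | No |
| Evaluation at 1 and 3 months (9.2) | Purpose not given | Unclear |
| Weekly, then monthly, Brief Follow-up report (9.2) | Form not shown | Unknown |
| Patient telephones (9.2) | Adverse effects | Yes, but unscheduled |

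**2. Which contacts fall within the 6 weeks (42 days).** Take a month as 30 days (an assumption).
- 1-month visit: 30 ± 8 = days 22 to 38, inside.
- 3-month visit: 90 ± 15 = days 75 to 105, outside.
- Weekly reports: 42/7 = 6, inside.

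The contacts needed to follow weakness through its stated duration therefore already exist. What the text lacks is a statement that they ask about it.

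**3. What incomplete capture would do (illustration only).** The documents give neither a true rate p nor a capture fraction s. With 16 patients, the chance of recording at least one event is 1 − (1 − p·s)^16.

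| True rate p | s = 100% | s = 50% | s = 25% |
|---|---|---|---|
| 10% | 0.81 | 0.56 | 0.33 |
| 20% | 0.97 | 0.81 | 0.56 |

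For example, p = 10% and s = 50% give 1 − 0.95^16 = 0.56.

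**4. What a by-hand test could show.** Exact McNemar uses only patients with an event in one hand and not the other. If all k such patients point the same way, the two-sided p = 2 × 0.5^k: k = 5 gives 0.0625 and k = 6 gives 0.031. At least 6 discordant patients, all in one direction, are needed for p < 0.05.

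**The case against.** The strongest reply is that the text shown does not establish a gap in practice. The Follow-up, Brief Follow-up and Adverse Event Forms are listed as attached and are not in the public document; any of them may ask about adverse events at every contact and record the hand. The evaluation at 1 and 3 months directly follows the bullet on adverse effects, so a safety purpose is plausible. The injection-day observation and the 48-hour call are not limited to the toxin, and a blinded assessor can note the hand and leave the link to allocation until unblinding. Section 8 also uses the word endpoint loosely: 8.1 describes when participation ends, and 8.2 goes straight on to the option to withdraw, so 8.2 may not have been meant as a counted outcome.

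Much of this stands, and it rules out several stronger readings that a reader might infer:

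- *That adverse events are asked about only up to 48 hours, or that harms will be under-counted.* The forms are unseen, patients can telephone, and the 1- and 3-month evaluation may serve this purpose. The text supports a risk, not a certainty.
- *That there is no control for local harms.* Every patient has a saline-injected hand, and placebo injections are observed. What is missing is a stated rule to record and compare by hand.
- *That only 2 of 42 days (5%) are covered.* This gives no value to the 1-month visit or the weekly reports, and weakness can be reported whenever it began.
- *That zero events in 16 patients, which leaves a one-sided 95% upper bound of 1 − 0.05^(1/16) = 17%, shows the defect.* That bound holds with perfect ascertainment; it reflects sample size.
- *That weakness is the main named risk.* Section 14.1 does not rank its list and states that no major risk is anticipated.

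The reply does not remove the point. An Adverse Event Form records events once they are known; its presence in a list does not say when patients are asked. The endpoint, visit schedule, data list and analysis are all in the text, and none of them supplies the later enquiry or the by-hand summary.

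**Conclusion.** The point holds as a weakness in the stated plan, worth correcting. The text states no structured adverse-event enquiry after the 48-hour call although it expects that weakness may last 6 weeks, words its safety endpoint around the toxin solution alone, and plans no summary of harms by hand. Later harms may be under-counted, and the toxin-hand versus saline-hand comparison is left unplanned.

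The extent of any under-count cannot be estimated from the documents; the capture figures above show only how quickly a trial of this size loses events if capture is partial. The conclusion assumes that the unseen forms do not already ask about adverse events at each contact and by hand. If they do, what remains is to align 8.2, 9.2, 9.4 and 11.1 with them.

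**What to change.** 1. Check the Follow-up, Brief Follow-up and Adverse Event Forms for an adverse-event question and a field for the hand.
2. In 8.2, define the safety endpoint as any adverse event after injection, recorded blinded as right hand, left hand or systemic, and linked to allocation at unblinding.
3. Unless the forms already do so, add an adverse-event question, including weakness in each hand, to the weekly and monthly Brief Follow-up report and to the 1-, 3-, 6- and 12-month Follow-up reports. State in 9.2 that these contacts include it, give the purpose of the 1- and 3-month evaluation, and add the item to 9.4.
4. In 11.1, report local events by toxin and saline hand in a descriptive paired table (both hands, toxin hand only, saline hand only, neither) and systemic events for the whole group. Exact McNemar is optional and should not carry the conclusion with 16 patients.

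The cost is at most one question on forms already in use, one small table, and a few more minor events to record. No visits are added.
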